7.3.1. Video-Conference Information

The CBT-I intervention and the assessments will take place over a video conference platform called Zoom (see details about privacy and security below in Section 10). Participants will be given a link to the session via email. At the end of the session the link will expire, and each new Zoom session will generate a new Zoom ID. Participants will be told to not enter their name but to enter their participant number to ensure confidentiality. We previously used telehealth systems embedded in the regional health authorities to conduct these assessments, but patients reported that this was still a barrier to participation because they had to travel (sometimes still quite a distance) to participate in the telehealth meeting. The use of Zoom will allow people to participate from the comfort of their own home and ensure privacy and equal access to treatment for Atlantic Canadians regardless of geography. Treatment sessions will be recorded to assess treatment fidelity and quality assurance.

- **7.4. Follow up Assessments:** Both groups will complete follow up assessments three and six months after completion of treatment to investigate durability of treatment effects.
- **7.5. Randomization:** Participants will be sequentially randomized to one of the two treatment conditions using a 1:1 allocation ratio created by the study biostatistician. The random allocation sequence will be prepared in advance and recorded on sequentially numbered, opaque, sealed and stapled envelopes to be provided to participants in order of study entrance. During the baseline assessment, the research coordinator will inform the participants which group they have been assigned to. All research personnel, including the PI, will be blind to the allocation sequence.

7.6. Data Collection Schema

The data collection schema for both groups are described in Tables 1a and 1b, followed by details about the instruments. The average time to complete the patient reported outcomes and neuropsychological measures at each assessment time is approximately 45-60 minutes. Participants in both the immediate treatment group and the waitlist treatment group will complete the sleep diaries. Participants will complete the sleep diary upon waking each morning for one week at each assessment period. The time to record the previous night's sleep is approximately 2 minutes. The research team has successfully conducted previous research with similar levels of participant burden. During the COVID-19 pandemic, participants will only complete the diaries if they are able to do so electronically (print and send back electronically, or fill out on their computer and email back). Participants who require a printed copy of the diary to be mailed will not complete the sleep diary component during the pandemic.

Table 1a. Schedule of Assessments and Outcome Collection for Immediate Treatment

Instrument	ТО	T1	T2	Т3	Т4	
	Baseline	Mid- Treatment	Post- Treatment	3 Month Follow Up	6 Month Follow Up	
CEQ	Х					
FACT-COG	X	X	X	X	X	
ISI	X	X	X	X	X	
MFSI-SF	X	X	X	X	X	
HADS	X	X	X	X	X	
WPAI	X		X	X	X	
Sleep Diaries*	X	X	X	X	X	
HLVT-R	X		X	X	X	
COWAT	X		X	X	X	
Digit Span	X		X	X	X	
BRIEF-A	X		X	X	X	
MMSE	X					
Adverse		X	X			
Events						
Protocol						

Table 1b. Schedule of Assessments and Outcome Collection for **Delayed Treatment**

Instrument	T0 Baseline	T1 Monitoring	T2 Pre- Treatment	T3 Mid- Treatment	T4 Post- Treatment	T5 3 Month Follow Up	T6 6 Month Follow Up
CEQ	Χ						
FACT-COG	X	X	X	X	X	X	X
ISI	X	X	X	X	X	X	X
MFSI-SF	X	X	X	X	X	X	X
HADS	X	X	X	X	X	X	X
WPAI	X		X		X	X	X
Sleep Diaries*	Х	Х	Х	Х	Х	Х	Х
HLVT-R	X		Х		Х	Х	Х
COWAT	Х		Х		Х	Х	Х
Digit Span	X		Х		Х	Х	Х
BRIEF-A	Χ		Х		Х	Χ	Х
MMSE	Х						
Adverse				Х	Х		
Events							
Protocol							

Medical history and demographics: A medical history and demographics questionnaire will be administered at the baseline assessment. This questionnaire will be used to obtain patient demographic information (e.g., sex, age, ethnic background, education, marital status, current employment status), medical history (e.g., type of cancer, dates of diagnosis and treatment, types of treatment received), psychiatric history, and current medication use. The Credibility/Expectancy Questionnaire (CEQ)^[38] will also be used at baseline to examine possible moderators of treatment effects.

Primary Outcome - The Functional Assessment of Cancer Therapy – Cognitive Function (FACT-Cog), version 3: The FACT-Cog will be used as the measure of perceived cognitive impairment. It is a 37-item questionnaire with four cognitive subscales: perceived cognitive impairments, impact on quality of life, comments from others, and perceived cognitive abilities. [20, 39] Responses range from 0, "never," to 4, "several times a day," in the previous 7 days. A change of 10.6-points has been established as clinically meaningful change on the FACT-Cog. [39-41]

Secondary Sleep Outcomes: The Insomnia Severity Index (ISI) has 7-items designed to specifically assess the severity of insomnia symptoms, the impact on daytime functioning, and the amount of associated distress.^[2] The ISI has established minimally important change values to ensure that the change is not only statistically significant, but also clinically meaningful to patients.

The Consensus Sleep Diary (CSD) provides a night-by-night, self-report of sleep duration, disruption, and perceived quality and will be used to capture more subtle variations in sleep. The sleep diary will be used to calculate sleep efficiency, sleep-onset latency, wake after sleep onset, total sleep time, time in bed, number of awakenings, sleep quality, and terminal wakefulness. Sleep diaries are considered a reliable and valid patient report of nightly insomnia symptoms. Participants will complete the sleep diary for one week at each assessment point. However, during the COVID-19 pandemic, participants will only complete the diaries if they are able to do so electronically (print and send back electronically, or fill out on their computer and email back). Participants who require a printed copy of the diary to be mailed will not complete the sleep diary component during the pandemic.

Neuropsychological Measures: The use of these measures adheres to the recommendations of the International Cognition and Cancer Task Force to improve research design and facilitate between-study comparisons and meta-analyses. [43]

The Mini-Mental State Examination (MMSE) is a method used for assessing cognitive metal state in clinical practice and in research.^[44] A score lower than 24 on the Mini-Mental State Examination suggesting the presence of severe cognitive impairments

The Hopkins Verbal Learning Test-Revised (HVLT-R) is a brief assessment of verbal learning and memory (immediate recall, delayed recall, delayed recognition). ^[45] The HVLT-R has six alternate forms available.

The Controlled Oral Word Association Test (COWAT) is a measure of verbal fluency, cognitive and motor speed, cognitive flexibility, strategy utilization, suppression of interference, and response inhibition. ^[46] The COWAT has two alternate forms available.

The Digit Span test is a subtest of the Wechsler Adult Intelligence Scale (WAIS) and the Wechsler Memory Scale (WMS)^[47]. The forward span captures attention efficiency and capacity, and the backward span is an executive task dependent on working memory^[47]. The digit span is not impacted by practice effects making is suitable for repeated testing^[48].

The Behaviour Rating Inventory of Executive Function-Adult (BRIEF-A) is composed of 75 items within nine non-overlapping theoretically and empirically derived clinical scales. It has 2 broad indexes (Behavioural Regulation and Metacognition), an overall summary score, and three validity scales (Negativity, Inconsistency, and Infrequency). The normative sample included 1,136 adults from a wide range of racial/ethnic backgrounds, educational backgrounds, and geographic regions. The BRIEF-A has demonstrated evidence of reliability, validity, and clinical utility as an ecologically sensitive measure of executive functioning in individuals with a range of conditions across a wide age range. A study that investigated the use of the BRIEF-A in patients with primary brain tumors suggests that measuring perceived executive dysfunction with the BRIEF-A is feasible.^[49]

Work Productivity Loss Measure: The Work Productivity and Activity Impairment (WPAI) questionnaire was developed for the purpose of collecting productivity loss data within clinical trials and is suitable for direct translation into a monetary figure. ^[50]

Additional Patient-Reported Outcomes: Fatigue will be measured using the Multidimensional Fatigue Symptom Inventory-Short Form (MFSI-SF).^[51] Anxiety and Depression will be measured using the Hospital Anxiety and Depression Scale (HADS) ^[52].

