- Meet the DSM-5 criteria for insomnia disorder and have a score of 8 or greater on the Insomnia Severity Index^[2]

- Have good performance status as indicated by an ECOG score of 0-2.
- Have high-speed internet connection, webcam, and are fluent using the internet

5.3. Exclusion Criteria:

5.3.1 For individuals with and without hematological malignancies:

- Another sleep disorder, besides insomnia, that is not adequately treated (ie: untreated obstructive sleep, sleep apnea)
- The presence of another psychological disorder that is not currently stable and/or would impair the ability to participate in the study
- A major sensory deficit (e.g. blindness)
- A neurologic or major medical condition known to affect cognitive function (e.g., Parkinson's)
- A history of cranial radiation
- A history of any other condition that may affect cognitive functioning (e.g., traumatic brain injury)
- Previous experience with CBT-I

Participants will not be excluded for using psychotropic medication prior to study entry (e.g. antidepressants) provided that the dose was not recently altered (stable over the previous 6 weeks). Considering the potential for prescription of medications to help with sleep (e.g. hypnotics, sedatives, and antidepressants) within the cancer population, medication use throughout the study will be tracked and adjusted for in the statistical analysis.

5.4. Early Withdrawal of Participants:

Any participant withdrawing their consent to participate in the study or their authorization to use their protected health information will be withdrawn from the study. Participants withdrawn may be replaced, at the discretion of the principal investigator.

Reasons why participants are withdrawn will be documented on the Study Termination Form. Every effort will be made to continue to collect data on every participant for the entire study duration regardless of whether the participant continues to complete assessments, assuming the participant has not withdrawn his/her authorization to obtain such information.

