At the mid and post treatment assessments, the participants will also be asked to complete questions related to adverse events during the CBT-I treatment. These questions will be added to their Qualtrics assessment. The open-ended Qualtrics responses will be thematically analyzed to create a record of adverse events experienced by the participants.

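### Section 5.3 promises to track medication use throughout the study and adjust for it, but no named instrument or visit records it after baseline, and the adjustment is undefined

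*Combined protocol and SAP*

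**What the plan says.** Section 5.3 allows participants on psychotropic medication if the dose was stable for six weeks before entry. It then looks ahead to use during the trial: "Considering the potential for prescription of medications to help with sleep (e.g. hypnotics, sedatives, and antidepressants) within the cancer population", it says, "medication use throughout the study will be tracked and adjusted for in the statistical analysis".

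Section 7.6 sets out what is collected and when: "The data collection schema for both groups are described in Tables 1a and 1b, followed by details about the instruments". The tables list instruments by visit, T0 to T4 for immediate treatment and T0 to T6 for delayed treatment. Neither has a row for medication. In the text after the tables, medication appears once, under medical history and demographics: "A medical history and demographics questionnaire will be administered at the baseline assessment". Its contents include "psychiatric history, and current medication use".

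Section 8.2 describes mixed-effects models for the primary question, intent-to-treat analysis, and sensitivity analyses for missing data. It mentions no medication variable.

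**The concern.** The primary comparison (section 8.2.1) sets the immediate arm after treatment against the delayed arm after its waiting period, which is T2 in both tables. Participants know their allocation, and the delayed arm waits 8 weeks without CBT-I. Some waitlist participants may start a sleep medicine in that time, and some CBT-I participants may reduce one. Section 5.3 itself expects such prescribing. These are co-interventions that act on sleep, and possibly on cognition, inside the randomised window.

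If use at T1 and T2 is not recorded, the report cannot show by arm what happened, and neither a positive nor a null FACT-Cog result can be examined for it. Such data cannot be reliably rebuilt at analysis.

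The second issue is the word adjusted. If post-baseline use were recorded and entered as a covariate in the primary model, the analysis would condition on something that treatment may have changed. That could bias the estimated effect of CBT-I.

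**Working it through.** No figure in the plan bears on this point, so the check sets the sections side by side. The question is whether any named instrument would yield medication data at T1 and T2, comparably in both arms.

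1. **Medical history questionnaire (section 7.6).** It records current medication and is given at baseline. It supplies T0 only.

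2. **Tables 1a and 1b.** There is no medication row. Counting visits after T0, four of five in the immediate arm (T1 to T4) and six of seven in the delayed arm (T1 to T6) have no stated medication source. T1 and T2 are the two that fall in the randomised window.

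3. **Sleep diary (section 7.6).** The variables to be calculated are sleep efficiency, sleep-onset latency and wake after sleep onset, and then "total sleep time, time in bed, number of awakenings, sleep quality, and terminal wakefulness". That makes eight, none of them medication. These are derived variables. The diary's items are not listed, and the note belonging to the asterisk on the diary row is not in the text available to us, so a medication entry cannot be excluded. Under section 7.6 the diary covers one week at each assessment, and during the pandemic participants who need a mailed copy do not complete it. Section 4.1 has the waitlist arm keeping diaries for 8 weeks and says nothing equivalent for the immediate arm.

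4. **Adverse-event questions (section 7.3).** At the mid- and post-treatment assessments, "the participants will also be asked to complete questions related to adverse events during the CBT-I treatment". Table 1a places them at T1 and T2. Table 1b places them at T3 and T4, after the waiting period has ended. Even if a medication change were mentioned in an open answer, nothing comparable would exist for the delayed arm before T2.

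5. **Entry rule (section 5.3).** The six-week stability requirement looks backwards from entry and gives no information after randomisation.

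6. **Analysis plan (section 8.2).** It names no medication variable, time point or model term. Adjustment for medication is stated only in section 5.3, which does not say whether baseline or later use is meant.

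Staff who followed the named instruments and visits would therefore hold baseline medication for everyone and no comparable record for T1 and T2.

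**The case against.** The two sections are not strictly contradictory. Section 5.3 commits to tracking, and section 7.6 says that the questionnaire is given at baseline without saying that medication is recorded only then. Absence from the tables is also weak evidence, because they omit the baseline questionnaire itself and so are not exhaustive. A log or diary item could exist outside them. This stands: the fault is a commitment that the schedule does not put into operation, and it is not proof that no data are collected.

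The objection also says that the primary result is safe. Under intent-to-treat, medication changes after randomisation are part of the strategies being compared, and the randomised contrast at T2 remains valid without these data. This stands too. A reader might infer that the gap undermines the primary analysis, but the documents do not support that.

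A reader might also want to state the likely shift in FACT-Cog. The documents give neither the rate of medication change in each arm nor its effect. Starts in one arm and reductions in the other need not act in the same direction, so the sign is unknown as well. Any figure would be assumption alone, and none is offered.

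What the objection does not remove is the need to act. If a log exists, it should be named and scheduled. If none exists, the window for collecting the data closes at T2. In either case the adjustment promised in section 5.3 remains undefined.

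**Conclusion.** The point holds as a gap between sections 5.3 and 7.6, together with an undefined adjustment. No named instrument or visit records medication after baseline, so changes in sleep or psychotropic medication before T2 could not be reported by arm from the schedule as written. It would go too far to say that the trial collects no such data, because an unlisted form or diary item may exist.

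The consequence is limited to describing co-intervention by arm and to a sensitivity analysis. Its effect on FACT-Cog cannot be sized from the documents. The change is still worth making, because it is cheap, the data cannot be reliably recovered later, and adjusting for post-baseline use in the primary model could bias the treatment effect. That last judgement assumes only that CBT-I may alter medication use.

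**What to change.** **Collection.** Add a short structured item to the Qualtrics form at T0, T1, T2 and every later visit in both arms. It should ask which sleep or psychotropic medicines are in recent use and, after T0, which were started, stopped or changed since the last assessment. Add the row to Tables 1a and 1b. If a medication log or diary item already exists, name it in section 7.6 and show its visits in both tables. The structured item is then needed only where that source does not cover T1 and T2 in both arms.

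**Analysis.** Amend sections 5.3 and 8.2 to say that only baseline medication use may be a covariate in the primary model. Post-baseline use is reported by arm and used only in a labelled sensitivity analysis, because it may be affected by treatment.

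**Cost.** About one minute per visit, so roughly 5 minutes in total in the immediate arm (five visits) and 7 in the delayed arm (seven visits), against the 45 to 60 minutes that section 7.6 gives for each assessment. The documents also need one row in two tables, a descriptive table and short edits to sections 5.3 and 8.2. The downside is the small extra burden on participants.

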8. STATISTICAL PLAN

8.1 Data Management: A data management system will be created by the principal investigator permitting tracking of data forms, computer-based editing and error-check, generation of periodic reports, and the creation of data sets for statistical analyses. All data will be stored in a fashion consistent with patient information privacy guidelines (see below). The data analysis sets will be exported to statistical software for analysis.

8.2. Data Analysis Plan

8.2.1. Analysis Plan: To answer our primary research question, we will use mixed-effects models to determine whether treated patients had greater improvements immediately post-treatment (primary endpoint) compared with patients in the control group after their waiting period. Then, data from both groups will be pooled together to assess, with a larger sample size, the durability of any effects observed at 6 months (secondary endpoint). This statistical procedure considers within-subject correlations from repeated measurements in the same subjects and allows estimation of between-group differences without necessitating last observation carried forward or exclusion of participants with missing data. Secondary and exploratory research questions will be answered using mediation/moderation analyses and/or additional mixed effects models.

The primary analyses will occur after the treatment completion (primary endpoint) and durability analyses will occur after the 6-month follow-up (secondary endpoint).

Subsidiary analyses will be conducted to examine the role of sex, gender, and sexual orientation in participant recruitment and retention, pre-treatment symptom severity, as well as the overall efficacy of online CBT-I, and results will be reported separately.

8.2.2. Missing Data: A drawback of any study is the risk of missing data and attrition bias. Our first line of defense will be to minimize the occurrence of missing observations, using a well-constructed study design, well-trained research staff, and acceptable subject burden.^[53] We will decrease barriers to recruitment/retention by scheduling study visits at a convenient time. For those who voluntarily withdraw from the study, we will record their reasons for withdrawing and use this information in a sensitivity analysis. To minimize missing data, all surveys will be checked right after completion. If needed, calls will be made to participants to complete missing data over the phone. For individuals who miss a study visit, RAs will call at least three times (morning/afternoon/evening) over the next week to try rescheduling the assessment.

Our second line of defense is to apply data analysis strategies that are as robust as possible to data losses. [54] Seeing that no universally accepted method exists for handling missing data, we will initially perform intent-to-treat analyses. We then will perform sensitivity analyses to evaluate the robustness of our results, including compete-case analysis, single imputation methods, such as last-observation and baseline carry forward analyses, and multiple imputation analyses. To avoid reporting bias, we will register our trial with ClinicalTrials.gov and follow the CONSORT recommendations for reporting randomized trials of nonpharmacological interventions. [55]

8.2.3 Sample Size Considerations: Our sample size is based on our primary outcome of PCI using the FACT-Cog immediately post-treatment. Since the primary outcome is continuous, we powered our trial using a t-test to detect the difference between two independent means for score at post-treatment. This is a conservative way to estimate sample size since the longitudinal analysis using the mixed-effects model specified in the analysis plan will provide greater power than a t-test. With power of 0.8 and two-sided alpha of 0.05, we will need at least 62 participants per treatment group and 124 in total to detect an effect size of 0.5.

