4. STUDY DESIGN

4.1. Overall Design: The proposed trial is an RCT of immediate treatment with CBT-I compared to a waitlist control for PCI in cancer survivors with insomnia (see Figure 2). Participants will receive individual CBT-I delivered by via online video-conferencing over the course of eight weeks. Participants in the waitlist control group will be required to monitor their sleep with sleep diaries for 8 weeks. They will receive CBT-I delivered by via video-conferencing immediately after the waiting period. Both groups will complete follow up assessments three and six months after completing treatment. The total study duration for the immediate and delayed treatment groups is 8 and 10 months, respectively. We chose a waitlist, or delayed treatment, control group because it would be unethical to refuse participants with insomnia the opportunity to receive CBT-I. The use of a waitlist control is also more representative of real-world health care in Canada, where patients will often have to wait for a certain amount of time before receiving treatment and will control for the regression to the mean.

Figure 2: Trial Design

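### Does the pooled 6-month durability analysis fail because no reference visit is named and the delayed arm has more than one visit before treatment?

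*Combined protocol and SAP*

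**What the plan says.** Section 8.2.1 compares the arms at the end of treatment (immediate arm) and the end of the wait (delayed arm) for the primary endpoint. It then says that "data from both groups will be pooled together to assess, with a larger sample size, the durability of any effects observed at 6 months", and labels this the secondary endpoint. Of the mixed-effects procedure in general it says that it "allows estimation of between-group differences without necessitating last observation carried forward or exclusion of participants with missing data".

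Section 7.4 sets the follow-up visits for both groups at "three and six months after completion of treatment to investigate durability of treatment effects". Section 4.1 explains that waitlist participants are treated after 8 weeks: "They will receive CBT-I delivered by via video-conferencing immediately after the waiting period". It adds that the waitlist "will control for the regression to the mean".

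The visits are in Tables 1a and 1b of section 7.6. FACT-Cog is collected at all five visits of the immediate arm and all seven of the delayed arm.

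**The concern.** Once the waitlist arm has been treated, a difference between the arms at 6 months no longer compares treated with untreated people. The pooled durability result must therefore be a within-person change, and section 8.2.1 does not say which. Two are open:

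- (a) from before treatment to 6 months, which shows how much gain remains;
- (b) from the end of treatment to 6 months, which shows how much has been lost.

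For (a), the delayed arm can be measured from T0 or from T2, on either side of the 8-week wait. Starting from T0 counts any untreated change as part of that arm's gain, and the protocol expects some such change, since it cites regression to the mean. The visit numbers do not help: T2 is after treatment in Table 1a and before it in Table 1b, while T4 is the 6-month visit in one table and the end of treatment in the other.

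If this were left fully open, the contrast for a named secondary endpoint could be picked once the results were known, and a favourable or an unfavourable account could be given from the same data.

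**Working it through.** **The plan's own figure.** Section 8.2.3 gives 62 per group for an effect size of 0.5, two-sided alpha 0.05 and power 0.80. The normal formula gives 2 × (1.960 + 0.842)² / 0.5² = 62.8, so 63 per arm; with 62 per arm the t-test power is 0.789. The stated number is reproduced to within one per arm. It concerns the post-treatment comparison only; no figure is given for durability.

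**Lining up the visits by their descriptive labels (Tables 1a and 1b).**

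| Phase | Immediate arm | Delayed arm |
|---|---|---|
| Entry | T0 | T0 |
| During the wait | none | T1 |
| Before treatment | T0 | T2 |
| Mid-treatment | T1 | T3 |
| End of treatment | T2 | T4 |
| 3 months | T3 | T5 |
| 6 months | T4 | T6 |

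Section 4.1 gives total durations of 8 and 10 months. That matches: about 2 months of treatment plus 6 is 8, and about 2 months of waiting plus 2 plus 6 is 10. The 6-month visit is thus unambiguous in each arm, and the delayed arm has a visit labelled as pre-treatment. Only the numbering clashes, not the labels.

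**T0 against T2 in the delayed arm.** Let w be the untreated change over the first 8 weeks, in SD units. Using T0 adds w to the delayed arm's change and, with equal arms, w/2 to the pooled change. The documents give no value for w. For assumed values of 0.1, 0.2 and 0.3 the shift is 0.05, 0.10 and 0.15 SD. To put this in points, assume an SD of 10.6 / 0.5 = 21.2, which treats the 10.6-point meaningful change in section 7.6 as equal to the 0.5 effect size; the protocol does not make that link. The shift is then 1.06, 2.12 and 3.18 points.

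**An example with both choices.** Assume a treatment gain of 0.5 SD, half of it kept at 6 months (0.25), and w = 0.2 in both arms.

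- T0 in both arms: 0.25 + 0.20 = 0.45 in each arm, pooled +0.45.
- T0 immediate, T2 delayed: (0.45 + 0.25) / 2 = +0.35.
- From the end of treatment: 0.25 − 0.50 = −0.25.

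Only 0.45 − 0.35 = 0.10 SD comes from T0 against T2. The gap from +0.35 to −0.25 is the difference between two questions. Naming T2 also does not clear the untreated change out: +0.35 still exceeds the 0.25 truly kept, because the immediate arm has only its entry visit as a start.

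**How often (a) is a significant gain and (b) a significant loss in the same trial.** Assumed: the between-group 0.5 taken as a within-person gain, equal SDs, the same correlation r between all visits, paired t-tests at two-sided 0.05, 20,000 simulated trials per cell. The SD of a change is √(2(1 − r)). As a hand check with half kept, r = 0.5 and n = 130, each test has expected t of about 0.25 × √130 / 1 = 2.85 against a critical value of 1.98, so power of about 0.81 each; the joint figure must be lower.

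| Share of gain kept | n | r = 0.5 | r = 0.7 | r = 0.8 |
|---|---|---|---|---|
| 50% (the peak) | 130 | 0.62 | 0.91 | 0.99 |
| 70% | 130 | 0.37 | 0.59 | 0.77 |
| 80% | 130 | 0.20 | 0.31 | 0.43 |
| 90% | 130 | 0.08 | 0.11 | 0.14 |
| 100% | 130 | 0.02 | 0.02 | 0.03 |
| 50% | 104 | 0.45 | 0.81 | 0.96 |
| 80% | 104 | 0.16 | 0.26 | 0.36 |

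The rows with n = 104 assume 20% missing at 6 months. The joint result is frequent when about a third to two thirds of the gain is kept and rare when nearly all is kept. When it occurs, both statements are true: people are better than before treatment and have slipped since it ended.

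**The case for a change.** The strongest case for a change is that this is the only endpoint section 8.2.1 labels as secondary, and that section 8.2.2 states an intention to avoid reporting bias. A mixed model estimates visit means; it does not choose which difference between them is the endpoint. The pre-treatment label on T2 settles the start of (a) at most, and says nothing about (a) against (b). One sentence, needing no new data, would close the gap.

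Much of this stands. No sentence in the documents names the reference visit or the contrast, and the choice between (a) and (b) cannot be deduced from the tables.

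It does not show, however, that the plan as written leads to a wrong result. Section 8.2.1 sets no faulty rule. The sentence on between-group differences describes the modelling procedure in general and need not govern the pooled step; the same section speaks of improvements and of repeated measurements within subjects. Nothing says that only one of (a) and (b) will be reported, or that a non-significant decline will be called durability, so a margin rule would answer an inference nobody has proposed. A fuller specification would still leave the sponsor to choose the contrast and would not supply a comparator.

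**Conclusion.** No change to the plan is needed. This is a gap in wording on one secondary endpoint that a competent analyst fills by aligning the arms on treatment phase: pre-treatment T0 / T2, end of treatment T2 / T4, 6 months T4 / T6 (immediate / delayed). The usual report then gives both the gain kept and the loss since treatment, as uncontrolled within-person changes.

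Misreading T0 as the delayed arm's start would cost half the untreated change, 0.05 to 0.15 SD under the assumed range, and would require ignoring a column label. The phase-aligned average carries the same amount through the immediate arm, so readers should not take it as a pure treatment effect under either choice. The joint probabilities, from 0.02 to 0.99, depend on assumed decay and correlation and describe compatible findings, not a contradiction. The primary comparison, the sample size and the data to be collected do not depend on any of this.
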